1	Antibiotics	Medical claim with an NDC, HCPCS, generic name or CPT code in the inpatient, non-IP, or pharmacy setting for antibiotic medications (dichotomous)	14 days prior to index date to 1 day prior to index date
1	Antifungal Medication	Medical claim with an NDC, HCPCS, generic name or CPT code in the inpatient, non-IP, or pharmacy setting for antifungal medications (dichotomous)	14 days prior to index date to 1 day prior to index date
1	Intravenous immunoglobulin	Medical claim with an NDC, HCPCS, generic name, CPT, or ICD-10 procedure code in the inpatient, non-IP, or pharmacy setting for intravenous immunoglobulin administration (dichotomous)	MM diagnosis to 1 day prior to index date

Objective	Variable	Definition	Assessment Period(s)
1	Other hematological malignancies	Medical claim with an ICD-10 code in the inpatient or non-IP setting for hematological malignancies other than MM (dichotomous)	MM diagnosis to 1 day prior to index date
1	Any non- hematological malignancy	Medical claim with an ICD-10 code in the inpatient or non-IP setting for non-hematological malignancies (dichotomous)	MM diagnosis to 1 day prior to index date
1	Plasma cell leukemia	Medical claim with an ICD-10 code in the inpatient or non-IP setting for plasma cell leukemia (dichotomous)	MM diagnosis to 1 day prior to index date
1	Bone lesions	Medical claim with an ICD-10 code in the inpatient or non-IP setting for bone lesions (dichotomous)	MM diagnosis to 1 day prior to index date
1	Peripheral neuropathy	Medical claim with an ICD-10 code in the inpatient or non-IP setting for peripheral neuropathy (dichotomous)	MM diagnosis to 1 day prior to index date
1	Any infection	Medical claim with an ICD-10 code in the inpatient or non-IP setting for any infection of the following types (dichotomous): COVID-19 Adenoviral pneumonia Cytomegaloviral pneumonitis COVID-19 pneumonia Other Pneumonia Upper respiratory tract infection Sepsis Cytomegaloviral infection Pneumocystis jiroveci pneumonia (PJP) Hepatitis C Hepatitis B Other infectious hepatitis Helicobacter pylori Candida esophagitis Urinary tract infection Sinusitis Bronchitis	MM diagnosis to 1 day prior to index date
1	Use of intravenous anti-infective	Medical claim with an NDC code generic name, CPT, or HCPCS code in the inpatient, non-IP, or pharmacy setting for anti-infective where the route	MM diagnosis to 1 day prior to index date

Objective	Variable	Definition	Assessment Period(s)

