	D 1	CI.	Nevirapine, Nevirapine, Nirmatrelvir/Ritonavir, Oseltamivir, Pemivibart, Penciclovir, Peramivir, Raltegravir, Remdesivir, Rilpivirine, Rimantadine, Ritonavir, Saquinavir, Simeprevir, Sofosbuvir, Stavudine, Tecovirimat, Tenofovir, Tenofovir, Tipranavi, Valaciclovir, Valacyclovir, Valganciclovir, Vilobelimab, Zanamivir, Zidovudine
Antibiotics	Baseline characteristic - Treatments	Claims data	HCPCS/CPT: 4041F, 4047F, 4048F, C9001, C9039, C9054, C9116, C9124, C9228, C9241, C9258, C9282, C9443, C9444, C9446, C9462, G8152, G8191, G8192, G8195, G8197, G8198, G8199, G8503, G8504, G8527, G8629, G8630, G9315, J0120, J0121, J0122, J0200, J0278, J0290, J0291, J0295, J0456, J0530, J0540, J0550, J0558, J0559, J0560, J0561, J0580, J0689, J0690, J0691, J0692, J0694, J0695, J0696, J0697, J0698, J0699, J0701, J0703, J0710, J0712, J0713, J0714, J0715, J0720, J0742, J0743, J0744, J0770, J0875, J0877, J0878, J1267, J1335, J1362, J1364, J1580, J1590, J1840, J1850, J1890, J1956, J2010, J2020, J2021, J2184, J2185, J2186, J2265, J2280, J2281, J2406, J2407, J2460, J2510, J2540, J2543, J2700, J2770, J2970, J3000, J3090, J3095, J3243, J3244, J3260, J3320, J3370, J3371, J3372, J7342, J7682, J7685, Q0144, S0016, S0021, S0024, S0030, S0032, S0034, S0039, S0040, S0072, S0073, S0074, S0077, S0081, S0085, S0142, S0143, J0457, J0688, J0687, J0736, J0737, J0872, J0873, J0874, J1271, J1836, J2290, J3374, J3375, J2183
			Generic names (and associated NDC codes): Penicillin, Tobramycin, Cycloserine, Vancomycin, Capreomycin, Cefazolin, Streptomycin, Neomycin, Bacitracin, Sulfadiazine, Isoniazid, Cefaclor, Loracarbef, Cefuroxime, Cephalothin, Cefamandole, Ceftazidime, Drotrecogin Alfa, Amoxicillin, Cephradine, Ampicillin, Sulfamethoxazole, Erythromycin, Dicloxacillin, Cloxacillin, Metronidazole, Tetracycline, Doxycycline, Cephalexin, Nitrofurantoin, Aztreonam, Oxacillin, Nafcillin, Cefepime, Sulfisoxazole, Trimethoprim, Sulfisoxazole Acetyl, Ceftriaxone, Erythromycin Ethylsuccinate, Cefixime, Sulfasalazine, Ethambutol, Pyrazinamide, Minocycline, Demeclocycline, Norfloxacin, Cefoxitin, Imipenem, Ertapenem, Ceftizoxime, Cefonicid, Ethionamide,

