			Tigecycline, Clindamycin, Lincomycin, Spectinomycin, Gentamicin, Cefpodoxime, Linezolid, Rifabutin, Gatifloxacin, Amikacin, Kanamycin, Cefadroxil, Cephapirin, Sulfanilamide, Sulfacetamide, Chloramphenicol, Dapsone, Polymyxin, Nalidixic Acid, Mafenide, Lomefloxacin, Mezlocillin, Ciprofloxacin, Ciprofloxacin Lactate, Moxifloxacin, Clofazimine, Mupirocin, Ticarcillin, Cefotetan, Cefotaxime, Silver Sulfadiazine, Levofloxacin, Oxytetracycline, Cefoperazone, Trovafloxacin Mesylate, Clarithromycin, Tinidazole, Ofloxacin, Doripenem, Sulfathiazole, Rifampin, Chloramphenicol Sod Succinate, Meropenem, Azithromycin, Cefdinir, Paromomycin, Colistin, Enoxacin, Sparfloxacin, Quinupristin, Netilmicin, Ceftibuten, Cefprozil, Rifapentine, Telithromycin, Daptomycin, Furazolidone, Bismuth Subsalicylate, Grepafloxacin, Piperacillin, Cefditoren, Ceftaroline Fosamil, Fosfomycin Tromethamine, Telavancin, Polymyxin B Sulfate, Gemifloxacin, Rifaximin, Sarecycline, Bacitracin, Chloramphenicol Palmitate, Chlortetracycline, Trimethoprim, Aminosalicylic, Pretomanid, Bacitracin Zinc, Fidaxomicin, Colloidal Bismuth Subcitrate, Omeprazole, Rifamycin, Dalbavancin, Cefiderocol, Bedaquiline, Oritavancin, Ceftolozane, Tedizolid, Plazomicin, Ozenoxacin, Delafloxacin Meglumine, Triamcinolone, Omadacycline, Eravacycline, Lefamulin, Ivermectin, Salicylic Acid
Antifungals	Baseline characteristic - Treatments	Claims data	HCPCS: J0285, J0286, J0287, J0288, J0289, 80285, J3465, J1450, J2248, J1835, J0637, J0348
			Generic name (and associated NDC codes): Amphotericin B, Voriconazole, Natamycin, Fluconazole, Micafungin, Posaconazole, Itraconazole, Caspofungin, Anidulafungin, Isavuconazole, Nystatin
Intravenous	Baseline	Claims	CPT: 90283
immunoglobulin	immunoglobulin characteristic - Treatments	data	HCPCS: C9072, C9130, C9270, G0332, J1459, J1554, J1556, J1557, J1566, J1568, J1572, J1576, J1599, Q4087, Q4088, Q4091, Q4092, Q4097, Q9941, Q9942, Q9943, Q9944
			ICD-10 Procedure: 30233S1, 30243S1, 30253S1, 30263S1
			NDC: 00026064012, 00026064020, 00026064071, 00026064512, 00026064515,

00026064520, 00026064524, 0002606 00026064612, 00026064620, 0002606 00026064625, 00026064671, 0002606	-
	64624. I
00026064625, 00026064671, 0002606	-
	64812,
00026064815, 00026064820, 0002606	64871,
00026064912, 00026064920, 0002606	64924,
00026064971, 00069101101, 0006910	01102,
00069110901, 00069110902, 0006912	22401,
00069122402, 00069131201, 0006913	31202,
00069141501, 00069141502, 0006915	55801,

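### Four non-antibiotic drugs stand as unrestricted names in the Annex 2 antibiotic list, so a single fill of any of them counts as antibiotic use at baseline

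*Protocol*

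**What the plan says.** Protocol section 9.3 refers the reader to Annex 2 for the full code list. The name-based part of the Antibiotics row there begins "Generic names (and associated NDC codes): Penicillin, Tobramycin, Cycloserine, Vancomycin". Further down the same comma-separated list come "Colloidal Bismuth Subcitrate, Omeprazole, Rifamycin" and "Delafloxacin Meglumine, Triamcinolone, Omadacycline, Eravacycline, Lefamulin, Ivermectin, Salicylic Acid". No text in the row limits any entry to a combination product, a formulation or a co-claimed antibiotic.

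Table 2 defines the variable as "Medical claim with an NDC, HCPCS, generic name or CPT code in the inpatient, non-IP, or pharmacy setting for antibiotic medications (dichotomous") and assesses it over "14 days prior to index date to 1 day prior to index date". It belongs to Objective 1. Exploratory Objective 3 replicates all objectives in the teclistamab cohort.

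Section 9.8 says that measures are coded from the codes and algorithms in the protocol and that the protocol is followed strictly.

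**The concern.** Omeprazole suppresses acid, triamcinolone is a corticosteroid, ivermectin is an antiparasitic and salicylic acid is a keratolytic. None is an antibiotic, so the code list disagrees with the variable it is meant to implement. The flag is dichotomous and one claim is enough. Each such claim from a patient with no true antibiotic claim in the window creates a false positive, and nothing in the list produces an offsetting error.

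The study is descriptive and makes no formal comparisons, so the reported percentage is itself the result. Its confidence interval reflects sampling error only and would not reveal the misclassification.

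**Working it through.** **Text check**

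1. *Are the four drugs separate entries?* Yes. Each stands between commas. The Antivirals row of the same annex joins nirmatrelvir and ritonavir with a slash, so the annex has a way to mark a combination. None of the four carries such a mark.
2. *Does an entry match on its own?* Yes. Table 2 accepts a match by generic name or by NDC, and the row header attaches NDC codes to each name without listing or restricting them.
3. *Is the placement deliberate?* Nothing suggests so. The Steroids definition names dexamethasone, methylprednisolone, prednisone and prednisolone but not triamcinolone, which is counted only as an antibiotic.
4. *Where else is the row used?* Annex 2 gives its role as a baseline treatment characteristic. The row for intravenous anti-infectives also points to it, but Table 2 limits that variable to intravenous administration. Infection outcomes are defined by ICD-10 codes.

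**Illustration of size**

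The protocol states no antibiotic-use rate, so there is no figure to reproduce. Let p be the true share of patients with an antibiotic claim in the window and q the share with a claim for any of the four drugs. Both are assumptions. If they are independent:

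- reported share = p + (1 - p)q
- bias = (1 - p)q

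| p | q | reported share | bias (points) |
|---|---|---|---|
| 20% | 2% | 21.6% | 1.6 |
| 20% | 5% | 24.0% | 4.0 |
| 20% | 10% | 28.0% | 8.0 |
| 20% | 15% | 32.0% | 12.0 |
| 40% | 2% | 41.2% | 1.2 |
| 40% | 5% | 43.0% | 3.0 |
| 40% | 10% | 46.0% | 6.0 |
| 40% | 15% | 49.0% | 9.0 |

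The bias runs from 1.2 to 12.0 points. Section 9.5 gives 133 patients with an elranatamab claim as of August 2024. At that size the bias is 0.012 × 133 = 1.6 to 0.12 × 133 = 16.0 patients.

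The 95% confidence half-width at n = 133 is 1.96 × √(p(1 - p)/133). This is 6.8 points at p = 20% and 8.3 points at p = 40%. Depending on q, the bias could be negligible or could exceed the sampling error.

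Without independence, bias = q minus the share of patients with both kinds of claim. For the p and q above, it can lie anywhere from 0 (all overlap) to q (no overlap).

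**The case against.** **The names may come from combination packs.** If the list was extracted from antibiotic products, the associated NDCs might already be limited to those packs, and Table 2 does speak of antibiotic medications. This is a plausible origin, but the protocol does not state it. It would also leave the separate match on generic name untouched. What stands is that the text does not say that every NDC of each ingredient is included; that is only the natural reading of an unrestricted phrase. The SAP was not available, and section 9.7 allows it to modify the protocol's plans. Section 9.3, however, places the full code list in Annex 2.

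**The size is assumed throughout.** This stands. The window counts claims, not possession. If fills last 30 days, a chronic user has a fill date inside the 14 days with probability about 14/30 = 47%; with 90-day fills it is 14/90 = 16%. For q to reach 15%, about 15/0.467 = 32% or 15/0.156 = 96% of patients would have to be chronic users (fill lengths assumed). Section 9.9 adds that over-the-counter purchases are not captured. The upper end of the range is therefore hard to reach, and regular use of such a drug does not translate directly into this window.

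**Stronger readings to avoid.** A reader might infer that the intravenous anti-infective variable is distorted too, because it points to the same list. The route restriction in Table 2 should keep oral and topical fills out. A reader might also infer that outcomes are affected. No eligibility, effectiveness, cost or adverse-event definition visible in the protocol uses this row. The supportive-medication list in Table 3 is not legible in the text available, so nothing can be said about it.

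**Conclusion.** The point holds for one variable. As written, the code list misclassifies claims for omeprazole, triamcinolone, ivermectin and salicylic acid as antibiotic use in the baseline description of both cohorts. The direction is certain: the percentage can only be overstated. The size cannot be determined from the protocol. The figure of about 1 to 12 points is an illustration that rests on assumed true use of 20-40%, an assumed 2-15% of patients with such a claim in the window, and independence between the two. The lower part of that range is easier to reach, given the short claim window.

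This is a descriptor, not an endpoint, so the consequence is limited. It is still a plain error in a primary-objective table, and it is easy to remove.

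**What to change.** In the Annex 2 Antibiotics row, delete omeprazole, triamcinolone, ivermectin and salicylic acid as stand-alone matches. Alternatively, keep them only as enumerated NDCs of products that also contain an antibacterial, and state that the generic name alone does not qualify.

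Removing these four will not by itself clean the row. Review the remaining entries for other non-antibacterials in the same pass; drotrecogin alfa, sulfasalazine and the bismuth salts are obvious candidates.

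The cost is a code-list edit and a re-run of one baseline variable per cohort. Version 2.0 already added codes to this row and corrected a mistyped code elsewhere in Annex 2, so the route exists. The change should be in place before the final analysis planned for 27 February 2026. Any interim table produced with the present list should note the difference.

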	Clinical, Adverse event		E13.41, G57.70, G57.71, G57.72, G57.73, G59, G57.80, G57.81, G57.82, G57.83, G58.8, G58.9, G64., G61.0, M05.50, M05.511, M05.512, M05.519, M05.521, M05.522, M05.529, M05.531, M05.532, M05.539, M05.541, M05.542, M05.549, M05.551, M05.552, M05.559, M05.551, M05.552, M05.559, M05.571, M05.572, M05.579, M05.59, E08.40, E08.42, E09.40, E09.42, E10.40, E10.42, E11.40, E11.42, E13.40, E13.42, G13.0, G13.1, A36.83, A52.15, G63, M34.83, G62.1, G61.1, G62.0, G62.2, G62.82, G61.81, G62.81, G61.89, G62.89, G61.9, G62.9, H46.3, M54.10, M54.18, M79.2, R20.0, R20.1, R20.2, R20.3, R20.8, R20.9
Any infection	Baseline characteristic - Clinical	Claims data	An ICD-10 Diagnosis Code for any of the following types of infections. See the rows below for codes for each infection type. COVID-19, Adenoviral pneumonia, Cytomegaloviral pneumonitis, Other Pneumonia, Upper respiratory tract infection, Sepsis, Cytomegaloviral infection, Pneumocystis jiroveci pneumonia (PJP), Hepatitis C, Hepatitis B, Other infectious hepatitis, Helicobacter pylori, Candida esophagitis, Urinary tract infection
Use of intravenous anti- infective	Baseline characteristic - Clinical	Claims data	See "Antivirals" and "Antibiotics" above
Neutropenia	Baseline characteristic - Clinical, Adverse event	Claims data	ICD-10 Diagnosis: D70x
Hypercalcemia	Baseline characteristic - Clinical	Claims data	ICD-10 Diagnosis: E83.52
Hypoxia	Baseline characteristic - Clinical, Adverse event	Claims data	ICD-10 Diagnosis: J96.20, J96.11, J96.90, J96.01, J96.00, J96.10, J96.21, J96.91, I27.23, R09.02
Hepatotoxicity	Baseline characteristic - Clinical, Adverse event	Claims data	ICD-10 Diagnosis: K71.x
Renal failure	Baseline characteristic -	Claims data	ICD-10 Diagnosis: N17x, N18x, N19x, R34x, T82.4, Z49.02, Z99.2

	Clinical, Adverse event		
Amyloidosis	Baseline characteristic - Clinical	Claims data	ICD-10 Diagnosis: E85.4x, E85.8x, E85.9x
Hypertension	Baseline characteristic - Clinical	Claims data	ICD-10 Diagnosis: I10x-I15x, I16x
Extramedullary disease	Baseline characteristic - Clinical	Claims data	ICD-10 Diagnosis: C90.2x
CCI score	Baseline characteristic - Clinical	Claims data	See components below
Myocardial infarction	Baseline characteristic - Clinical	Claims data	ICD-10 Diagnosis: I21.x, I22.x, I25.2
Congestive heart failure	Baseline characteristic - Clinical	Claims data	ICD-10 Diagnosis: I11.0, I13.0, I13.2, I25.5, I42.0, I42.5, I42.6, I42.7, I42.8, I42.9, I43.x, I50.x, P29.0
Peripheral vascular disease	Baseline characteristic - Clinical	Claims data	ICD-10 Diagnosis: I70.x, I71.x, I73.1, I73.8, I73.9, I77.1, I79.0, I79.1, I79.8, K55.1, K55.8, K55.9, Z95.8, Z95.9
Cerebrovascular disease	Baseline characteristic - Clinical	Claims data	ICD-10 Diagnosis: G45.x, G46.x, H34.0x, H34.1x, H34.2x, I60.x, I61.x, I62.x, I63.x, I64.x, I65.x, I66.x, I67.x, I68.x
Dementia	Baseline characteristic - Clinical	Claims data	ICD-10 Diagnosis: F01.x, F02.x, F03.x, F04, F05, F06.1, F06.8, G13.2, G13.8, G30.x, G31.0x, G31.1, G31.2, G91.4, G94, R41.81, R54
Chronic pulmonary disease	Baseline characteristic - Clinical	Claims data	ICD-10 Diagnosis: J40.x, J41.x, J42.x, J43.x, J44.x, J45.x, J46.x, J47.x, J60.x, J61.x, J62.x, J63.x, J64.x, J65.x, J66.x, J67.x, J68.4, J70.1, J70.3
Rheumatic disease	Baseline characteristic - Clinical	Claims data	ICD-10 Diagnosis: M05.x, M06.x, M31.5, M32.x, M33.x, M34.x, M35.1, M35.3, M36.0
Peptic ulcer disease	Baseline characteristic - Clinical	Claims data	ICD-10 Diagnosis: K25.x, K26.x, K27.x, K28.x

Liver disease	Baseline characteristic - Clinical	Claims data	ICD-10 Diagnosis: B18.x, K70.0, K70.1, K70.2, K70.3, K70.9, K71.3, K71.4, K71.5, K71.7, K73.x, K74.x, K76.0, K76.2, K76.3, K76.4, K76.8, K76.9, Z94.4, I85.0x, I86.4, K70.4x, K71.1x, K72.1x, K72.9x, K76.5, K76.6, K76.7
Diabetes	Baseline characteristic - Clinical	Claims data	ICD-10 Diagnosis: E08.0x, E08.1x, E08.6x, E08.8x, E08.9x, E09.0x, E09.1x, E09.6x, E09.8x, E09.9x, E10.0x, E10.1x, E10.6x, E10.8x, E10.9x, E11.0x, E11.1x, E11.6x, E11.8x, E11.9x, E13.0x, E13.1x, E13.6x, E13.8x, E13.9x, E08.2x, E08.3x, E08.4x, E08.5x, E09.2x, E09.3x, E09.4x, E09.5x, E10.2x, E10.3x, E10.4x, E10.5x, E11.2x, E11.3x, E11.4x, E11.5x, E13.2x, E13.3x, E13.4x, E13.5x
Renal disease	Baseline characteristic - Clinical	Claims data	ICD-10 Diagnosis: I12.9, I13.0, I13.10, N03.x, N05.x, N18.1, N18.2, N18.3, N18.4, N18.9, Z94.0, I12.0, I13.11, I13.2, N18.5, N18.6, N19.x, N25.0, Z49.x, Z99.2
Hemiplegia or paraplegia	Baseline characteristic - Clinical	Claims data	ICD-10 Diagnosis: G04.1, G11.4, G80.0, G80.1, G80.2, G81.x, G82.x, G83.x
Human immunodeficiency virus	Baseline characteristic - Clinical	Claims data	ICD-10 Diagnosis: B20.x
Metastatic solid tumor	Baseline characteristic - Clinical	Claims data	ICD-10 Diagnosis: C77.x, C78.x, C79.x, C80.0, C80.2
Use of premedication	Outcome - Dosing and Administration Patterns	Claims data	HCPCS: J1094, J1096, J8540, J1100, J0131, J7637, J7638, J7312, J1200, Q0163 Generic names (and associated NDCs): Acetaminophen, Dexamethasone, Diphenhydramine
Inpatient	Baseline characteristic, Outcome - HCRU	Claims data	Any event in the inpatient table or an event in the non-inpatient table where acute_subacute is "acute inpatient" or where utilization type is "professional services", and service subcategory contains the term "hospital/IP encounter"
Outpatient	Baseline characteristic, Outcome - HCRU	Claims data	Any event in the non-inpatient table where utilization type is outpatient and service subcategory is not "emergency dept encounter"

Emergency department	Baseline characteristic, Outcome - HCRU	Claims data	Any event in the non-inpatient table where utilization type is "outpatient" and service subcategory is "emergency dept encounter"
Cytokine release syndrome (CRS)	Safety events	Claims data	ICD-10 Diagnosis: D89.83x
Immune effector cell- associated neurotoxicity Syndrome (ICANS)	Adverse events	Claims data	ICD-10 Diagnosis: G92.0x
Anemia	Adverse events	Claims data	ICD-10 Diagnosis: D46.0, D46.1, D46.20, D46.21, D46.22, D46.4, D46.9, D46.A, D46.B, D46.C, D46.Z, D47.4, D50.0, D50.1, D50.8, D50.9, D51.0, D51.1, D51.2, D51.3, D51.8, D51.9, D52.0, D52.1, D52.8, D52.9, D53.0, D53.1, D53.2, D53.8, D53.9, D55.0, D55.1, D55.2, D55.21, D55.29, D55.3, D55.8, D55.9, D59.0, D59.1, D59.10, D59.11, D59.12, D59.13, D59.19, D59.2, D59.3, D59.30, D59.31, D59.39, D59.4, D59.5, D59.6, D59.8, D59.9, D60.0, D60.1, D60.8, D60.9, D61.01, D61.09, D61.1, D61.2, D61.3, D61.810, D61.811, D61.818, D61.82, D61.89, D61.9, D63.0, D63.1, D63.8, D64.9, D75.81
Lymphopenia	Adverse events	Claims data	ICD-10 Diagnosis: D72.810
Hypogammaglobulinemia	Adverse events	Claims data	ICD-10 Diagnosis: D80.1, D80.3, D80.9
Hypophosphataemia	Adverse events	Claims data	ICD-10 Diagnosis: E83.39
Hypokalaemia	Adverse events	Claims data	ICD-10 Diagnosis: E87.6
Arthralgia	Adverse events	Claims data	ICD-10 Diagnosis: M25.5x
Pyrexia	Adverse events	Claims data	ICD-10 Diagnosis: R50.x
Hypotension	Adverse events	Claims data	ICD-10 Diagnosis: I95.0, I95.81, I95.89, I95.9, I95.2
Fatigue	Adverse events	Claims data	ICD-10 Diagnosis: R53.x, G93.3x

Nausea or vomiting	Adverse events	Claims data	ICD-10 Diagnosis: R11.x
Diarrhea	Adverse events	Claims data	ICD-10 Diagnosis: R19.7, K59.1
Rash	Adverse events	Claims data	ICD-10 Diagnosis: R21, D72.12
Angioedema	Adverse events	Claims data	ICD-10 Diagnosis: T78.3X, D72.118
Erythema	Adverse events	Claims data	ICD-10 Diagnosis: L53.0, L53.1, L53.2, L51, L52, L71.0, L71.1, L71.8, L93.0, L93.2, L49.0, L49.1, L49.2, L49.3, L49.4, L49.5, L49.6, L49.7, L49.8, L49.9, L00, L26, L30.4, L53.8, L92.0, L95.1, L98.2, L53.9
Muscle spasms	Adverse events	Claims data	ICD-10 Diagnosis: M62.83X
Musculoskeletal pain	Adverse events	Claims data	ICD-10 Diagnosis: M25.50, M25.522, M25.551, M25.552, M25.561, M25.562, M25.572, M25.579, M25.59, M25.612, M25.621, M25.629, M25.631, M25.641, M25.642, M25.662, M25.669, M25.671, M25.673, M25.674, M25.675, M25.676, M54.6, M54.81, M79.1, M79.12, M79.18, M79.621, M79.622, M79.631, M79.639, M79.641, M79.644, M79.646, M79.669, M79.671, M79.673, M79.675, M25.511, M25.512, M25.519, M25.521, M25.529, M25.531, M25.532, M25.539, M25.541, M25.542, M25.549, M25.611, M25.619, M25.622, M25.632, M25.639, M25.649, M25.651, M25.659, M25.672, M25.69, M25.671, M25.69, M25.672, M25.69, M25.672, M25.69, M25.672, M27.69, M27.603, M79.604, M79.605, M79.606, M79.609, M79.629, M79.632, M79.672, M79.674, M79.676
COVID-19	Adverse event - infection	Claims data	ICD-10 Diagnosis: U07. 1

COVID-19 pneumonia	Adverse event -	Claims	ICD-10: J12.82
Adenoviral pneumonia	infection Adverse event - infection	data Claims data	ICD-10 Diagnosis: J12.0
Cytomegaloviral pneumonitis	Adverse event - infection	Claims data	ICD-10 Diagnosis: B25.0
Other pneumonia	Adverse event - infection	Claims data	ICD-10 Diagnosis: A01.03, A02.22, A20.2, A21.2, A31.0, A37.01, A37.11, A37.81, A37.91, A43.0, A48.1, B01.2, B05.2, B06.81, B37.1, B38.0, B38.2, B39.0, B39.2, B58.3, B59, B77.81, J10.00, J10.08, J11.00, J11.08, J12.1, J12.2, J12.3, J12.81, J12.89, J12.9, J13, J14, J15.0, J15.1, J15.20, J15.211, J15.212, J15.29, J15.3, J15.4, J15.5, J15.6, J15.7, J15.8, J15.9, J16.0, J16.8, J17, J18.0, J18.1, J18.8, J18.9, J85.1
Upper respiratory tract infection	Adverse event - infection	Claims data	ICD-10 Diagnosis: J20.9, J00.0, J04.0, J06.0, J06.9, J02.9
Sepsis	Adverse event - infection	Claims data	ICD-10 Diagnosis: A02.1, A32.1, A40.7, A40.0, A40.1, A40.3, A40.8, A41.9, A41.01, A41.02, A41.1, A41.2, A41.3, A41.4, A41.50, A41.51, A41.52, A41.53, A41.59, A41.81, A41.89, A42.9, A54.7, B37.86, R65.7, R65.20, A22.21, A26.7, A41.7, A41., A41.0, A41.5, P36.8, P36.0, P36.10, P36.19, P36.2, P36.30, P36.39, P36.4, P36.5, P36.8
Cytomegaloviral infection	Adverse event - infection	Claims data	ICD-10 Diagnosis: B25.0, B25.1, B25.2, B25.8, B25.9, B27.0, B27.1, B27.2, B27.9
РЈР	Adverse event - infection	Claims data	ICD-10 Diagnosis: B59
Hepatitis C	Adverse event - infection	Claims data	ICD-10 Diagnosis: B17.1x, B18.2, B19.2x
Hepatitis B	Adverse event - infection	Claims data	ICD-10 Diagnosis: B16.x, B17.0, B18.0, B18.1, B19.1x
Other infectious hepatitis	Adverse event - infection	Claims data	ICD-10 Diagnosis: B17.2, B17.8, B17.9, B18.8, B18.9, B19.0, B19.9
Helicobacter pylori	Adverse event - infection	Claims data	ICD-10 Diagnosis: B96.81
Candida esophagitis	Adverse event - infection	Claims data	ICD-10 Diagnosis: B37.81
Urinary tract infection	Adverse event - infection	Claims data	ICD-10 Diagnosis: N39.0

Document Approval Record

Document Name:

C1071044_NON-INTERVENTIONAL STUDY PROTOCOL_V2_06AU G2025

Document Title:

C1071044_NON-INTERVENTIONAL STUDY PROTOCOL_V2_06AU G2025

Signed By:	Date(GMT)	Signing Capacity
Redacted	02-Sep-2025 15:50:58	Final Approval
Redacted	03-Sep-2025 15:07:21	Manager Approval

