5. AMENDMENTS AND UPDATES

Version Identifier	Date	Amendment Type (substantial or administrative)	Protocol Section(s) Changed	Summary of Amendment(s)	Reason
V 2.0	06 August 2025	Substantial	Abstract	The study end date and corresponding data availability period were updated. Two additional interim analyses were added.	The study period was extended to increase sample size and follow-up time for analysis.
V 2.0	06 August 2025	Substantial	Milestones	The study end date and corresponding data availability period were updated. Two additional interim analyses were added.	Same as above
V 2.0	06 August 2025	Substantial	Study Design	The end date for data availability was changed from March 2025 to December 2025.	Same as above
V 2.0	06 August 2025	Substantial	Data Source	The study end date and corresponding data availability period were updated. Two additional interim analyses were added.	Same as above

V 2.0	06 August 2025	Substantial	ANNEX 2. ADDITION AL INFORMA TION	HCPC codes for IV antibiotics were added to the 'Antibiotics' section	Additional HCPC codes for IV Anti-Infectives were identified and added to the overall Antibiotics category
V 2.0	06 August 2025	Substantial	Data Analysis	Added mandatory template text about separate SAP.	Separate SAP was be developed.
V 2.0	06 August 2025	Substantial	Title page	Active substance and Medicinal product rows	Updated to match Pfizer template requirement.
V 2.0	06 August 2025	Substantial	9.6.1. Case Report Forms/Data Collection Tools/Electr onic Data Record and 9.6.2. Record Retention	Sections 9.6.1 and 9.6.2 removed.	Per template instructions: Sections 9.6.1 and 9.6.2 should be deleted for studies with no human review of unstructured data; these are studies in which either of the following occurs: • All study data exist as structured data by the time of study start • The conversion of unstructured data to structured data during the implementation of the protocol is performed solely by a computer using automated/algorithm ic methods, such as natural language processing.
V 2.0	06 August 2025	Substantial	List of Abbreviatio ns	Abbreviations added	AE, EC, ESRD, CMS, SAP and VRDC were missing

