		of administration is intravenous for an intravenous anti-infective (dichotomous)	
1	Neutropenia	Medical claim with an ICD-10 code in the inpatient or non-IP setting for neutropenia (dichotomous)	MM diagnosis to 1 day prior to index date
1	Hypercalcemia	Medical claim with an ICD-10 code in the inpatient or non-IP setting for hypercalcemia (dichotomous)	MM diagnosis to 1 day prior to index date
1	Hepatotoxicity	Medical claim with an ICD-10 code in the inpatient or non-IP setting for hepatotoxicity (dichotomous)	MM diagnosis to 1 day prior to index date
1	Renal failure	Medical claim with an ICD-10 code in the inpatient or non-IP setting for renal failure (dichotomous)	MM diagnosis to 1 day prior to index date
1	Amyloidosis	Medical claim with an ICD-10 code in the inpatient or non-IP setting for amyloidosis (dichotomous)	MM diagnosis to 1 day prior to index date
1	Hypertension	Medical claim with an ICD-10 code in the inpatient or non-IP setting for hypertension (dichotomous)	MM diagnosis to 1 day prior to index date
1	Extramedullary disease	Medical claim with an ICD-10 code in the inpatient or non-IP setting for extramedullary disease (dichotomous)	MM diagnosis to 1 day prior to index date
1	Charlson Comorbidity Index (CCI) score	CCI ¹⁸ (continuous and categorical): • 0 (no comorbidities) • 1 to 2 (mild) • 3 to 4 (moderate) • ≥ 5 (severe)	180 days prior to index date to index
1	Myocardial infarction	Medical claim with an ICD-10 code in the inpatient or non-IP setting for myocardial infarction (dichotomous)	180 days prior to index date to index
1	Congestive heart failure	Medical claim with an ICD-10 code in the inpatient or non-IP setting for congestive heart failure (dichotomous)	180 days prior to index date to index date

Objective	Variable	Definition	Assessment Period(s)
1	Peripheral vascular disease	Medical claim with an ICD-10 code in the inpatient or non-IP setting for peripheral vascular disease (dichotomous)	180 days prior to index date to index
1	Cerebrovascular disease	Medical claim with an ICD-10 code in the inpatient or non-IP setting for cerebrovascular disease (dichotomous)	180 days prior to index date to index
1	Dementia	Medical claim with an ICD-10 code in the inpatient or non-IP setting for dementia (dichotomous)	180 days prior to index date to index
1	Chronic pulmonary disease	Medical claim with an ICD-10 code in the inpatient or non-IP setting for chronic pulmonary disease (dichotomous)	180 days prior to index date to index

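### Annex 2 gives 'Use of intravenous anti-infective' no antifungal codes although Table 2 does not limit the drug class, so patients whose only IV anti-infective was an antifungal are recorded as 'no'

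*Protocol*

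**What the plan says.** Section 9.3, Table 2, lists 'Use of intravenous anti-infective' as a yes/no characteristic under Objective 1. It counts a claim by NDC, generic name, CPT or HCPCS code in the "pharmacy setting for anti-infective where the route" and, after a page break, "of administration is intravenous for an intravenous anti-infective (dichotomous". The window runs from myeloma diagnosis to one day before index. The class is simply anti-infective, with no restriction to antibacterials or antivirals.

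Section 9.3 refers the reader to Annex 2 for the full code list. The Annex 2 row for this variable contains only a cross-reference: "See 'Antivirals' and 'Antibiotics' above".

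Annex 2 has a separate Antifungals row, with HCPCS entries "J0285, J0286, J0287, J0288, J0289, 80285, J3465, J1450, J2248, J1835, J0637, J0348" and generic names "Amphotericin B, Voriconazole, Natamycin, Fluconazole, Micafungin, Posaconazole, Itraconazole, Caspofungin, Anidulafungin, Isavuconazole, Nystatin". The intravenous anti-infective row does not mention it.

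The amendment log in section 5 adds context: "Additional HCPC codes for IV Anti-Infectives were identified and added to the overall Antibiotics category". The newly identified IV codes went into the general list. Annex 2 contains no list limited to the intravenous route.

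**The concern.** The definition and the code list for one variable do not cover the same drugs. Table 2 sets two conditions, class (any anti-infective) and route (intravenous). The Annex entry is narrower than Table 2 on class, because antifungals are missing. It is wider on route, because the referenced rows are not divided by route.

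The class gap is the firm problem. Adding the route filter cannot repair it, because a filter only removes claims and cannot bring in codes that were never listed. At stake is whether a reported Objective 1 characteristic measures what its name and definition say.

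**Working it through.** The plan states no figure for this variable, so there is none to reproduce. The check compares the lists.

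**Step 1: class, by HCPCS/CPT code.** Transcribing the three Annex 2 rows gives:

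| Annex 2 row | Distinct HCPCS/CPT entries | Referenced by the IV anti-infective row |
|---|---|---|
| Antibiotics | 143 | yes |
| Antivirals | 28 | yes |
| Antifungals | 12 | no |

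The Antifungals entries share 0 of 12 codes with the other two rows combined.

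**Step 2: class, by generic name.** None of the 11 antifungal names appears in the Antibiotics or Antivirals rows. Under the cross-reference, no listed antifungal can set the variable to 'yes' by any route.

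**Step 3: does another variable fill the gap?** Table 2 has an 'Antifungal Medication' variable, but it covers only the 14 days to 1 day before index and is not limited by route. It cannot recover IV antifungal use since myeloma diagnosis.

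**Step 4: direction and size of the error.** Let A be the patients with an IV antibiotic or antiviral in the window, F those with an IV antifungal, and N the cohort size.

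- Proportion that Table 2 describes: |A ∪ F| / N
- Proportion that the Annex codes can return with the route condition applied: |A| / N
- Shortfall: |F not in A| / N

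Patients who had both kinds of drug are still counted correctly. The error runs one way and equals the share with IV antifungals only. The protocol gives no value for that share. Purely as assumptions, shares of 2%, 5% and 10% would understate the proportion by 2, 5 and 10 percentage points. At N = 133 that is 0.02 × 133 = 2.7, 0.05 × 133 = 6.7 and 0.10 × 133 = 13.3 patients. The 133 is the August 2024 count of patients with an elranatamab claim, before eligibility criteria and before the study period was extended. It serves here as a scale only, not as the analysis cohort.

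**Step 5: route.** The Antibiotics and Antivirals rows list generic names with their associated NDCs and no route restriction. The Antibiotics names include amoxicillin, cephalexin and mupirocin and end with "Omadacycline, Eravacycline, Lefamulin, Ivermectin, Salicylic Acid". No code in either row is marked as intravenous. Table 2's condition therefore has to be applied separately to each claim or NDC.

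**The case against.** The strongest reply is that Table 2 and Annex 2 have different jobs. Section 9.3 puts the definition in the table and the codes in the Annex, and section 9.8 says measures are coded from both codes and algorithms. A source list wider than the filtered variable is then not a contradiction, because Table 2 removes the oral claims. This stands. A reader might infer that oral antibiotics and antivirals qualify, so that the variable becomes little more than any use of such drugs since diagnosis. The documents do not support that. It would happen only if the Annex row were programmed alone, against both the definition and the variable's own name.

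A second reply is that section 9.7 leaves detailed methodology to the SAP, which is not shown and may state how route is assigned. That is fair for the route rule, so its absence is a secondary remark here. It does not answer the class mismatch, because the protocol itself fixes both the definition and the code list, and section 9.8 says the protocol will be strictly followed.

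A third reply is that leaving antifungals out may be a deliberate scope choice, loosely worded in Table 2. That is possible, and it would change which passage to edit. The two passages would still need to be reconciled.

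**Conclusion.** The mismatch is real and follows from the text alone. Table 2 covers any intravenous anti-infective, the Annex codes cannot capture an antifungal, and patients whose only IV anti-infective was an antifungal are misclassified as 'no'. This rests on two premises: that 'anti-infective' in Table 2 carries its ordinary meaning, which includes antifungals, and that the Annex is used as the code list, as section 9.3 says. The mixed-route rows are a weaker, related point: the intravenous condition is stated, but no listed code is marked to satisfy it.

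The size cannot be derived from the protocol. It is the IV-antifungal-only share, and the 2% to 10% range above is assumed.

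The reach is narrow. The variable is one descriptive baseline characteristic. It is not used for eligibility, outcomes, subgroups or sample size, and the study makes no formal comparisons. A reader might take it as the study's baseline marker of serious infection. The protocol gives it no such role, and Table 2 has a separate 'Any infection' variable over the same window that includes sepsis and several pneumonias.

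**What to change.** Choose one of two reconciliations.

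- **If antifungals are in scope:** replace the Annex 2 entry with codes and NDCs of intravenous route taken from the Antivirals, Antibiotics and Antifungals rows, subject to the Table 2 route condition. The criterion should be intravenous, not merely injectable, since the broader term would create a new mismatch with Table 2.
- **If antifungals are deliberately out of scope:** rename the variable and narrow Table 2 to intravenous antivirals and antibiotics. The Annex row should then point to the intravenous-route codes within those two rows.

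The cost is small: one code-list row under the first option, or the variable's name and definition plus that row under the second. The claims are already held, so no new data are needed. Version 2.0 already corrected codes in Annex 2, so an edit of this kind is routine.
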